#### Randomization Procedures

After consent is obtained, the diagnostic interview will be administered and if determined eligible, participants will then complete the baseline assessment. After the assessment, the

participant will be randomized to one of the two study conditions, stratified by site. The research assistant conducting the assessment will thus be blind to the participant's study condition. We will randomize individuals within stratification groups in permuted blocks, ensuring that the intervention and control samples will be the same size once every block has been randomized. This procedure maximizes statistical power.

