### Assertive Outreach

EnCoRE includes ongoing, active outreach to bolster intrinsic motivation to remain engaged and to communicate that the program is available to assist them when they encounter barriers to achieving their community engagement goals. Outreach activities include: (1) Additional individual MI sessions if needed to reevaluate community engagement goals and problem-solve barriers to trying new community activities, (2) Brief meetings with a participant - such as meeting the participant at the medical center for coffee or a walk around the complex to foster a good relationship and to address and work through any reservations or fears about coming to the program, (3) Community visits with participants (visiting nearby community locations) if needed to assist the participant in trying a new community activity, (4) Linking participants with other professionals if they need assistance with issues related to benefits, transportation, housing, or other services as a way to build the treatment relationship, especially if such issues are seen by the participant as more important in the short-term than other EnCoRE related goals.

In either condition, a reminder letter will be sent to participants who either have started to attend groups but are absent or who have never started groups, and whom we have been unable to reach by phone or in person. If needed, study staff will attempt to schedule participants for their consent or assessments by approaching them at their upcoming VA appointments, as noted in their CPRS medical record. Additionally, a reminder letter will be sent to participants who are scheduled for a consent appointment or due to complete a post-treatment or follow-up assessment but whom we have been unable to reach by phone or in person. If a participant expresses to study staff they he or she is having difficulty attending study

appointments due to lack of transportation then a bus token, or equivalent travel voucher, will be offered to the participant.

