## **5.5 Study Evaluations**

Table 3 Domain	Measure (time for administration)	Time-point
-------------------	-----------------------------------	------------

Diagnosis	Structured Clinical Interview for DSM-IV  - Mood Disorders and Psychotic Symptoms Sections (SCID)(60 minutes)	BL
Symptoms	Clinical Assessment Interview for Negative Symptoms  (CAINS); Brief Psychiatric Rating Scale (24-item version)  (BPRS)(60 minutes)	BL, PT, FU
Social/Community Functioning Recovery/Self-efficacy	Role Functioning Scale (RFS); Social Functioning Scale (SFS);  Brief University of California San Diego Performance-based Skills Assessment (UPSA)  Maryland Assessment of Recovery Survey (MARS)  Community Reintegration of Service Members Computer Adaptive Test  (CRIS-CAT); Quality of Life (TL-30S) (20 minutes)	BL, PT, FU
Attitudes/Beliefs	Success and Resource Appraisals Questionnaire Dysfunctional Attitudes Scale (DAS I and II)  Future Thinking Task  (15 minutes)	BL, PT, FU
Attendance/Satisfaction	Participant Satisfaction Questionnaire and Service Satisfaction Scale  Qualitative interview (10 minutes)	PT, FU
Feasibility/Acceptability	Recruitment and retention of participants, Attendance and participation data, Information from qualitative interviews from Veterans and providers, EnCoRE interventionist logs and supervision notes	Ongoing Qualitative Interviews: PT
Adherence and Competence	Adherence Rating Scale, Competence Rating Scale; Completed by blinded coders.	Ongoing
Substance Abuse	Michigan Alcoholism Screening Test  , Drug Abuse Screening Test  (5 minutes)	BL,
Cognitive functioning	Weschler Test of Adult Reading, Brief Cognitive Assessment (15 minutes)	BL,
Other	Demographics Form, Clinic Services Use Tracking Form (CSUTF), Morisky Medication Index  , Medication Use, Service Use Form (SUF)  (10 minutes)	BL, PT, FU

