Secondary Aim 1: Test the efficacy of EnCoRE in producing positive changes at PT and FU on a second measure of social/community functioning (UPSA-B). Hypothesis 3 (H3): Veterans exposed to EnCoRE will have higher mean scores than controls at post-treatment and at FU on the UPSA-B total score.

Secondary Aim 2: Test the efficacy of EnCoRE in producing positive changes at PT and FU on mental health recovery. Hypothesis 4 (H4). Veterans exposed to EnCoRE will have higher mean ratings on the MARS than control at PT and FU. Analysis models for H4 will be parallel to those for H1.

Secondary Aim 3: Assess the modifying effect of covariates on the effectiveness of EnCoRE including general cognitive ability and psychotic symptoms. Hypothesis 5 (H5): General cognitive ability and symptoms of psychosis will not impact the effectiveness of the intervention

for negative symptoms and community functioning at PT and FU (See analysis below for H6). Hypothesis 6 (H6): Greater ratings of consumer participation in and satisfaction with the intervention will be associated with better PT and FU outcomes. For each of the potential modifiers in H5 and H6, we will re-fit the primary analysis model for PT outcomes after adding two terms, the potential modifier and the interaction term between the treatment condition indicator (Tx condition) and the potential modifier. The variable will be a modifier if the coefficient for the interaction term is statistically significant ( $p$ -value<.05). A similar model will be used to assess modification at FU but there will be additional interaction terms with time (including 3-way interaction time\*treatment condition\*modifier), in order to estimate modifying effects at FU (i.e. separate effects at FU vs. PT).

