#### Other analyses

To examine feasibility and acceptability we will 1) Track measures of engagement and participation by recording: a) actual recruitment as compared to recruitment goals, to determine the pace at which subjects consent to participate; b) rates of engagement and attendance at intervention sessions, and the number of reminder and other outreach contacts required to keep participants engaged. This will tell us how much staff time is required to get participants to remain involved; c) Track VA clinic service and medication use with the CSUTF and the SUF after post and follow-up assessments by conducting chart reviews. 2) Track costs, including: a) Training of research therapists in the intervention; b) Payments for session attendance. Attendance at training sessions and information on training session duration will be recorded by project staff. We will determine inter-rater reliability for the adherence and competence scales, then calculate mean adherence ratings for intervention congruent and noncongruent behaviors and mean competence ratings. 3) Review supervision notes and interventionist logs to identify content for implementation materials via discussion among the investigators. We will examine CRIS-CAT responses and explore reliability/validity in a schizophrenia sample.

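### H6 is stated as an association, but its decision rule looks only at a treatment-by-modifier interaction on post-randomisation attendance and satisfaction

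*Protocol*

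**What the plan says.** H6 appears twice in the protocol, under Hypotheses in section 3.0 and under Secondary Aim 3 in section 5.6: "Greater ratings of consumer participation in and satisfaction with the intervention will be associated with better PT and FU outcomes". The aim above it is to "Assess the modifying effect of covariates on the effectiveness of EnCoRE including general cognitive ability and psychotic symptoms". One paragraph serves both H5 and H6. It re-fits the primary post-treatment model after "adding two terms, the potential modifier and the interaction term between the treatment condition indicator (Tx condition) and the potential modifier", and then decides: "The variable will be a modifier if the coefficient for the interaction term is statistically significant", at p<.05. The follow-up version adds interactions with time.

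On timing, Randomization Procedures (section 5.1) states that after the baseline assessment the "participant will be randomized to one of the two study conditions, stratified by site". In the table in section 5.5, the Attendance/Satisfaction row ("Participant Satisfaction Questionnaire and Service Satisfaction Scale") is scheduled at post-treatment and follow-up, with no baseline value. Participation is tracked through "rates of engagement and attendance at intervention sessions" (section 5.6, Other analyses). Under Assertive Outreach, "EnCoRE includes ongoing, active outreach to bolster intrinsic motivation to remain engaged"; reminder letters go to both arms.

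H7, the neighbouring association hypothesis, is handled differently: change scores in the EnCoRE condition are correlated and tested against zero. The SAP lists only baseline moderators (DAS, SARA-Q and CAINS MAP) and does not mention H6.

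**The concern.** There are two separate difficulties.

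First, the test does not match the hypothesis. H6 is about a slope: more participation or satisfaction goes with a better outcome. The rule examines a difference between two slopes. The comparison arm also has 24 group sessions, so attendance can be measured in both arms and similar slopes are plausible. In that case H6 is true and the quantity tested is zero.

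Second, if effect modification is really what is meant, the variables are unsuitable. Attendance and satisfaction come after randomisation, refer to two different programmes, and may be influenced by arm (EnCoRE has its own outreach) or by the outcome (satisfaction is rated when the outcome is measured). A significant interaction could then arise although the treatment effect is the same for everyone.

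At stake is a secondary claim. The trial could find no support for an association that exists, or label satisfaction a modifier of EnCoRE when it only marks who did well.

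**Working it through.** **The plan's own figure.** No size or power is stated for H6, so the check starts from the sample-size paragraph for H1 and H2: two-sided alpha .025, power .80, d = .50, baseline to post-treatment correlation .63, 15% attrition.

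- Per arm: 2 × ((2.241 + 0.842)/0.50)² × (1 − .63²) = 45.86.
- Total with attrition: 2 × 45.86/0.85 = 107.9, so 108, as stated. With correlation .70 the result is 91.2, so 92, also as stated.
- Expected post-treatment assessments per arm: 108 × 0.85/2 = 45.9.

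**What the rule tests.** Write the model as Y2 = a + b·Y1 + site + c·Tx + m·M + k·Tx·M.

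- Control slope on M: m.
- EnCoRE slope on M: m + k.
- The rule uses k alone. If the two slopes are equal, k = 0 whatever the size of m.

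**Power, by Fisher z.** Assumptions: two-sided .05 (the protocol does not state sidedness); r is the correlation of modifier and outcome after adjustment for baseline; r = .20, .30 or .40 in EnCoRE and 0 in control. These values of r are in neither document. With n per arm:

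- Within EnCoRE: Φ(atanh(r) × √(n − 3) − 1.96)
- Interaction: Φ(atanh(r)/√(2/(n − 3)) − 1.96)

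| r in EnCoRE | atanh(r) | Within EnCoRE, n = 45.9 | Interaction, n = 45.9 |
|---|---|---|---|
| .20 | .2027 | Φ(1.328 − 1.96) = 26% | Φ(0.939 − 1.96) = 15% |
| .30 | .3095 | Φ(2.027 − 1.96) = 53% | Φ(1.434 − 1.96) = 30% |
| .40 | .4236 | Φ(2.775 − 1.96) = 79% | Φ(1.962 − 1.96) = 50% |

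At follow-up, with the planned 80% retention, n = 108 × 0.80/2 = 43.2 and the same formulas give 25%, 50% and 77% within EnCoRE, and 15%, 28% and 48% for the interaction.

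**Equal slopes.** The model was simulated with 92 assessed participants, unit SDs, correlation .63, a treatment effect of −0.5, site omitted and 5,000 runs per scenario. The true slope was the same in both arms, in outcome SDs per SD of the modifier:

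| Slope in both arms | Interaction rejects | Within-EnCoRE test rejects |
|---|---|---|
| −0.2 | 5.0% | 40% |
| −0.3 | 5.1% | 70% |
| −0.4 | 5.1% | 89% |
| −0.5 | 4.9% | 98% |

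These slopes are not on the scale of r above. A slope of 0.3 corresponds to a partial r of 0.3/√(0.3² + 1 − .63²) = .36. The mismatch also runs the other way: with no association in EnCoRE and a slope of +0.4 (adverse) in control, the interaction rejects in 65% of runs.

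**False modifiers.** Here the modifier has no effect and the treatment effect is constant. With everything null, the interaction rejected in 4.5% of runs.

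| Assumed mechanism, in EnCoRE only | Strength .3 | .5 | .7 |
|---|---|---|---|
| An unmeasured prognostic factor drives participation | 17% | 39% | 66% |
| Satisfaction reflects the outcome | 29% | 68% | 95% |

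In the first row the factor's coefficient on the outcome residual is set at −.7. Both rows depend on the mechanism acting in one arm only. If the modifier is unaffected by arm and outcome and is equally confounded in both arms, the interaction is not biased.

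**The case against.** The strongest reply is that the SAP already confines moderators to baseline variables, so the flawed analysis may never be run. That is true of the SAP's list. But the SAP neither withdraws H6 nor gives it another test. One reader might infer that the protocol rule still binds, another that H6 was abandoned; the documents say neither.

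A reader might infer that the model cannot address H6, or that H6 would be rejected when true. Neither quite follows. The EnCoRE slope is main effect plus interaction, so it can be estimated, and the rule says when a variable counts as a modifier rather than when H6 fails. What stands is that no other criterion for H6 is written down.

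Or modification may be the intended target, since H6 sits under that aim. Then the post-randomisation timing is the difficulty. If the intervention in H6 means EnCoRE alone, the modifier is undefined in controls and the interaction cannot be estimated. No reading rescues the rule.

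A reader might also set the interaction's 5% under equal slopes against the power of a pooled two-arm test, about 82% at r = .30: Φ(.3095 × √85.8 − 1.96). That overstates the gain. The remedy is a within-EnCoRE test, with 53% at that r, and it too is confounded: in the false-modifier scenarios it rejected more often than the interaction did.

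Finally, it is tempting to say that the primary results or the later implementation trial would be misdirected. H1 to H4 are tested without these modifiers, and the protocol ties the later trial to the qualitative interviews, not to H6.

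**Conclusion.** The concern holds as a mismatch between hypothesis and decision rule, with a second problem of interpretation. Under equal slopes the rule rejects at about its 5% null rate although H6 is true; this follows from the model and does not depend on the assumed slope. When the association exists only in EnCoRE, the rule has roughly 15% to 50% power against 26% to 79% for a direct test, for assumed r from .20 to .40 at post-treatment. A significant interaction cannot be read as effect modification, because the modifiers follow randomisation and nothing in the plan secures the conditions under which bias vanishes. The size of that bias is not established: the simulated rates illustrate assumed one-arm mechanisms. H6 is secondary and the trial was not powered for it, so the point should be corrected but does not touch H1 to H4 or the sample size of 108.

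**What to change.** - Take H6 out of the modifier paragraph in the protocol (sections 3.0 and 5.6) and state that the intervention in H6 means EnCoRE.
- Test H6 within the EnCoRE arm: regress the post-treatment outcome, and separately the follow-up outcome, on its baseline value, site and attendance. Fit satisfaction in a separate model. Report the slope with its 95% confidence interval and label it a non-causal association. This brings H6 into line with the within-EnCoRE approach of H7.
- Keep treatment-by-modifier models for variables measured at baseline: those for H5, and the SAP's baseline moderators.
- Have the SAP carry this analysis or state that H6 was dropped.

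The cost is wording in two documents and one simple regression per outcome, time point and measure. The downside is that the result is openly associational and has modest power, about 53% at r = .30 at post-treatment, so the interval matters more than the p-value.

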Hypothesis 6 (H6): Greater ratings of consumer participation in and satisfaction with the intervention will be associated with better PT and FU outcomes. For each of the potential modifiers in H5 and H6, we will re-fit the primary analysis model for PT outcomes after adding two terms, the potential modifier and the interaction term between the treatment condition indicator (Tx condition) and the potential modifier. The variable will be a modifier if the coefficient for the interaction term is statistically significant (p-value<.05). A similar model will be used to assess modification at FU but there will be additional interaction terms with time (including 3-way interaction time\*treatment condition\*modifier), in order to estimate modifying effects at FU (i.e. separate effects at FU vs. PT).

Hypothesis 7 (H7): Improvements on ratings of attitudes/beliefs (e.g. DBS, FTT score) in the EnCoRE condition from BL to PT and FU will be positively associated with improvements in symptom and functioning outcome measures from BL to PT and FU, respectively. Change scores will be computed for attitudes/beliefs and recovery, and for symptom and functioning scales. Pearson correlations will be calculated and significance tests of the null hypothesis of zero correlation will be conducted. Note: These tests of association can be conducted even if improvement on ratings of self-efficacy and recovery are not significant in H3.

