Secondary	The Role Functioning Scale (RFS, Goodman et al., 1993) is a reliable and valid interview that assesses four domains: Working Productivity, Independent Living/Self Care, Family Network Relationships, and Immediate Social Network Relationships (e.g., Edmondson et al., 2012, Yamada et al., 2010). In the present analysis, we summed ratings of Independent Living/Self Care, Family Network Relationships, and Immediate Social Network Relationships as our measure of role functioning. We excluded Working Productivity because our sample was comprised largely of adults who were retired or not working.	Role Functioning Scale	Baseline-24 weeks
Secondary	Brief University of California San Diego Performance-based Skills Assessment (UPSA; Mausbach et al., 2007) assesses the respondent's capacity to perform tasks similar to those encountered in daily life in two domains: 1) financial skills, in which participants are required to count change, make change from an item purchased at a store, and write a check for a utility bill, and 2) communication skills, in which participants are asked to demonstrate how to use a telephone to dial emergency services, call information to ask for a telephone number, and call a physician to reschedule a medical appointment. For each domain, the total percent correct is calculated and converted to a standardized score ranging from 0 to 50. A summary score is then calculated by summing the two domain scores (range = 0–100), with higher scores indicating better functional capacity.	UPSA-B Total Score	Baseline-24 weeks
Secondary	The 25-item Maryland Assessment of Recovery Survey (MARS; Drapalski et al., 2012) assesses personal recovery in serious mental illness with items addressing having control over one's life, strength to meet and solve challenges, and belief in one's abilities (e.g., "I have abilities that can help me reach my goals", "I am able to set my own goals in life", "I can influence important issues in my life").	MARS Total Score	Baseline-24 weeks

Statistical Analysis Plan

Statistical Analysis Overview: Proposed sample size of N = 108 was chosen to detect a standardized mean difference in change from baseline to post-treatment equal to 0.50 between the intervention and active control arms. There were two primary outcome scales – one measuring social functioning and the other measuring negative symptoms. Threshold for statistical significance was $p < 0.05$ with no adjustment for multiple comparisons.

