
Statistical Test of Hypothesis: The analysis of the primary outcomes utilized a mixed effects model accounting for a random therapy group effects and the analysis included all available data at baseline, post-treatment, and follow-up time-points. Error terms across time points were assumed correlated with unstructured correlation matrix. To test time-specific hypotheses, terms in the mean model included separate indicators for post-treatment and follow-up time points, and interaction terms between these indicators and condition. Based on randomization to treatment condition, the model assumed no differences at baseline, i.e. any differences were assumed to be due to random sampling error. All continuous outcome scales were checked for skew, and an appropriate transformation was applied as needed. Statistical significance was defined as $p \leq .05$. All analyses were performed using SAS version 9.4. In moderator analyses we examined whether treatment effects on the primary outcomes (CAINS MAP, SFS) differed according to baseline dysfunctional attitudes measured by the DAS and SARA-Q. We also examined whether baseline negative symptoms (CAINS MAP) modified treatment effects for the SFS. Each moderator variable was dichotomized at the median. In separate models, the moderator and interaction terms with the moderator were added to the primary linear mixed effects models to test whether treatment effects at post-treatment and follow-up time points differed for those above versus below the median.

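### Moderator tests number 16 to 24 in the protocol and 5 to 10 in the SAP, all at an unadjusted .05 with no exploratory label; the protocol also turns each result into a yes/no declaration

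*Protocol*

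**What the plan says.** **Protocol.** The rule appears twice in the same words, under Hypotheses in section 3.0 (H6) and under Secondary Aim 3 in section 5.6: "The variable will be a modifier if the coefficient for the interaction term is statistically significant", with p below .05. It covers each potential modifier in H5 (cognitive ability, psychotic symptoms) and H6 (participation, satisfaction). The primary model is refitted for post-treatment, and a model with time interactions gives a separate modifying effect at follow-up. No multiplicity adjustment is given for these tests. The only allowance for multiple testing in the protocol is in Sample Size Considerations, where alpha is halved to .025 because two primary hypotheses are tested.

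**SAP.** Statistical Analysis Overview: "Threshold for statistical significance was $p < 0.05$ with no adjustment for multiple comparisons". Statistical Test of Hypothesis: the moderator analyses ask whether effects on the two primary outcomes "differed according to baseline dysfunctional attitudes measured by the DAS and SARA-Q". A third moderator follows: "We also examined whether baseline negative symptoms (CAINS MAP) modified treatment effects for the SFS". Each moderator is split at its median, and interaction terms are added to the mixed model "to test whether treatment effects at post-treatment and follow-up time points differed for those above versus below the median". That paragraph puts significance at p of .05 or less.

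Neither document describes any of these analyses as exploratory or hypothesis-generating. The protocol lists its set as a secondary aim with named hypotheses.

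**The concern.** A rule that makes a variable a modifier whenever one coefficient passes .05 leaves no room for how many coefficients were examined. Applied over a dozen or more interactions, it will often return a modifier when none exists. Without an exploratory label, that result would enter the report with the same standing as a planned secondary finding.

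What is at stake is what the trial may say about who benefits from EnCoRE. The primary comparisons are not affected. The protocol's own practice makes the gap visible: two primary hypotheses were thought to need a divided alpha in the sample-size calculation, while the larger set of interaction tests receives neither an adjustment nor a caution.

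**Working it through.** **1. The plan's own figure.** No familywise error rate is stated for the moderator tests, so there is none to reproduce. The one calculation that allows for multiplicity is the sample size (d = .50, alpha .025 taken as two-sided, power .80, 15% attrition). Per arm, n = 2(2.241 + 0.842)²(1 − r²)/.50².
- r = .70: 38.8, so 39 per arm; 78/.85 = 91.8, so 92. Stated: 92.
- r = .63: 45.9 per arm; 91.7/.85 = 107.9, so 108. Stated: 108. (Rounding up to 46 per arm first gives 109.)

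Both figures reproduce, so the halved alpha was really used for H1 and H2.

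**2. Count of tests.**
- Protocol: 4 variables × 2 outcomes (CAINS subscale and one functioning scale) × 2 times = 16. With both SFS and RFS, as in H2, 4 × 3 × 2 = 24. That is 4 to 6 tests per variable.
- SAP: DAS 2 outcomes × 2 times = 4; SARA-Q 2 × 2 = 4; baseline CAINS-MAP 1 × 2 = 2. The total is 10 over three moderators, or 2 to 4 per moderator. With one joint test of post-treatment and follow-up per moderator-outcome pair, the total is 5.

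Each named modifier is counted as one variable. Section 5.1 also names depression and attitudes/beliefs as potential moderators, and section 5.6 adds a check of baseline severity by treatment. These are left out of the count.

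**3. Chance of at least one p below .05 with no true modification, independent tests:** 1 − .95^k.

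| Set | k | Chance |
|---|---|---|
| SAP, joint tests | 5 | 1 − .774 = 22.6% |
| SAP, separate times | 10 | 1 − .599 = 40.1% |
| Protocol, 2 outcomes | 16 | 1 − .440 = 56.0% |
| Protocol, 3 outcomes | 24 | 1 − .292 = 70.8% |

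**4. Correlated tests.** The documents give no correlations, so the following are assumptions, evaluated by multivariate-normal simulation with two-sided .05 tests.
- SAP, 10 tests, one common correlation of .3, .5, .7 or .8: 35.1%, 28.7%, 21.2%, 17.2%.
- SAP, 10 tests, structured correlation (moderators 0 to .7, outcomes 0 to .7, time points .3 to .8): 23.6% to 38.7%.
- Protocol, 16 to 24 tests, structured correlation (moderators 0 to .5, outcomes .3 to .7, time points .5 to .8): 36% to 66%. With 24 tests and a common correlation of .8: 23.9%.
- One protocol variable with 4 to 6 tests, structured correlation: 13% to 24%.

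**5. How large a significant interaction must be.** Take the protocol's r = .63, 46 completers per arm and a median split giving four cells of 23. This uses the ANCOVA variance from the sample-size section as a stand-in for the SAP's mixed model. The treatment-effect SE is √(2 × .603/46) = .162 SD. The interaction SE is √(4 × .603/23) = .324 SD. Significance then needs an estimate of 1.96 × .324 = .63 SD or more, above the .50 main effect the trial was sized for. Power for a true interaction of .50 is Φ(.50/.324 − 1.96) = about 34%. An interaction that passes .05 is therefore either a chance result or likely to be overestimated.

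**The case against.** The case for leaving the text alone has real substance.
- The .05 is a per-test level, openly stated. No familywise rate is promised for modifiers, and the SAP says plainly that it does not adjust. This stands.
- The protocol places these analyses under a secondary aim and powers the trial for H1 and H2 only. Many statisticians would report secondary moderator tests unadjusted. This stands as an argument against compulsory adjustment. It does not justify a rule that declares a modifier from one p-value.
- The declaration rule belongs to the protocol's H5/H6 variables. The SAP examines other moderators and has only a general significance threshold. So the rule and the 10 tests must not be run together, and they are counted separately here.
- The SAP does not say whether post-treatment and follow-up are tested jointly. If they are, its set is 5 tests, not 10.
- H5 predicts no modification, so a false positive there would contradict the study's hypothesis rather than support it. Participation and satisfaction arise after randomization, so they could not be used to select patients at entry.

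Three stronger readings are tempting, and the documents do not support them. A reader might infer that each moderator receives at least 10 tests; ten is the SAP total over three moderators. A reader might infer a single multiple of a stated 5%, such as six times; no such familywise 5% is stated, and any one multiple depends on correlations that the documents do not give. A reader might infer that moderator results will decide whom the larger implementation trial targets; the Abstract, section 3.0 and Specific Aim 3 tie that trial to the qualitative interviews.

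**Conclusion.** The point holds as a fault in the declaration rule and in the missing exploratory label, not as a breach of a promised error rate. With no true modification, the SAP set yields at least one nominally significant moderator with probability 40% (10 independent tests), roughly 17% to 39% (10 tests under assumed correlations) or 23% (5 independent joint tests). The protocol's set gives 56% to 71% if independent, and less under correlation. These figures rest on the test counts above, two-sided .05 tests and, for the ranges, correlations that are assumed rather than documented. Under every assumption examined, a chance modifier is common enough that an unadjusted p-value cannot establish one. The primary conclusions are untouched, so this is an inexpensive improvement to what the trial may claim.

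**What to change.** - In the protocol (Hypotheses in 3.0, and Secondary Aim 3 in 5.6), delete the sentence that makes a variable a modifier at p below .05.
- In both those places and in the SAP's Statistical Test of Hypothesis, state that all moderator analyses, H5/H6 and the SAP set alike, are exploratory and hypothesis-generating. Report every interaction estimate with its 95% CI, give the number of tests run, and make no claim of established effect modification from an unadjusted p-value.
- Optional: use one joint post-treatment and follow-up interaction test per moderator-outcome pair, which reduces the SAP set from 10 to 5.
- If a confirmatory modifier claim is wanted, adjust (for example by Holm) over all moderator tests actually run. Adjusting over the SAP's 10 alone would leave out the H5/H6 variables that the declaration rule governs.

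The cost is wording; no new data are needed. The SAP is written in the past tense, so the change may fall mainly on the report. The downside is that a real modifier becomes harder to declare, though its estimate and interval are still shown.
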